5.3.2.1. Hepatitis B Reactivation

Hepatitis B virus (HBV) reactivation, in some cases resulting in fulminant hepatitis, hepatic failure, and death, can occur in patients treated with anti-CD20 antibodies such as obinutuzumab. HBV reactivation has been reported in patients who are hepatitis B surface antigen (HBsAg) positive and also in patients who are HBsAg negative but are hepatitis B core antibody (anti-HBc) positive. Reactivation has also occurred in patients who appear to have resolved hepatitis B infection (i.e., HBsAg negative, anti-HBc positive, and hepatitis B surface antibody [anti-HBs] positive). HBV reactivation is defined as an abrupt increase in HBV replication manifesting as a rapid increase in serum HBV DNA level or detection of HBsAg in a person who was previously HBsAg negative and anti-HBc positive. Reactivation of HBV replication is often followed by hepatitis, i.e., increase in transaminase levels and, in severe cases, increase in bilirubin levels, liver failure, and death.

Positive serology for Hepatitis B is defined as positivity for Hepatitis B surface antigen (HBsAg) or Hepatitis B core antibody (anti-HBc). Screen all patients for HBV infection by measuring HBsAg and anti-HBc before initiating treatment with obinutuzumab. For patients who show evidence of hepatitis B infection (HBsAg positive [regardless of antibody status] or HBsAg negative but anti-HBc positive), consult physicians with expertise in managing hepatitis B regarding monitoring, and consideration for HBV antiviral therapy.

Monitor patients with evidence of current or prior HBV infection for clinical and laboratory signs of hepatitis or HBV reactivation during and for several months following treatment with obinutuzumab. HBV reactivation has been reported for other CD20-directed cytolytic antibodies following completion of therapy.

In patients who develop reactivation of HBV while receiving obinutuzumab, immediately discontinue obinutuzumab and any concomitant chemotherapy, and institute appropriate treatment. Resumption of obinutuzumab in patients whose HBV reactivation resolves should be discussed with physicians with expertise in managing hepatitis B. Insufficient data exist regarding the safety of resuming obinutuzumab in patients who develop HBV reactivation.

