For the subset of patients who are Hepatitis B viral DNA-negative and anti-HBc positive and have undetectable Hepatitis B viral DNA levels at screening, Hepatitis B viral DNA levels must be followed approximately every 4 weeks. Guidelines for the management of hepatitis B reactivation are outlined in Table 1.

Table 4. Management of Hepatitis B Reactivation

Hepatitis B Viral DNA Level by Real-Time PCR	Guideline
> 100 IU/mL	
• Hold obinutuzumab• Begin anti-viral medication and treat for at least 1 year after the last dose of obinutuzumab.• Immediately refer the patient to a gastroenterologist or hepatologist for management.• Resume obinutuzumab once Hepatitis B viral DNA levels decrease to undetectable levels.
> 100 IU/mL while on anti-viral medication	Discontinue obinutuzumab.
29–100 IU/mL	
Retest within 2 weeks.
 
If still hepatitis B viral DNA positive:
 
• Hold obinutuzumab• Begin anti-viral medication and treat for at least 1 year after the last dose of obinutuzumab.• Immediately refer the patient to a gastroenterologist or hepatologist for management• Resume obinutuzumab once Hepatitis B viral DNA levels decrease to undetectable levels

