- **Vital Signs:** Vital sign measurements should include: blood pressure, heart rate, temperature, respiration rate, and oxygen saturation.
- **Complete Blood Count:** 5-part differential, hemoglobin, white blood cell count (WBC), platelet count, absolute neutrophil count (ANC), and absolute lymphocyte count (ALC) are required at each time point as described in the schedule of events. Direct antiglobulin test and % reticulocyte count are required at screening only.

CBC performed \leq 72 hours prior to D1 of each cycle can be used in lieu of repeating on D1.

- **Coagulation Panel:** activated partial thromboplastin time (aPTT) and prothrombin time or INR (PT/INR).
- **Chemistry:** LDH, creatinine, urea (BUN), potassium, sodium, chloride, bicarbonate, glucose,

alkaline phosphatase, AST, ALT, phosphorus, total bilirubin, direct bilirubin (if total bilirubin is elevated only), albumin, uric acid are required.

Chemistry performed \leq 72 hours prior to D1 of each cycle can be used in lieu of repeating on D1.

- **Urinalysis:** performed per institutional standards.
- **β 2-microglobulin:** performed per institutional standards
- **Hepatitis Screening:** hepatitis B surface antigen and hepatitis C antibody are required. Results from within 12 months prior to the first dose of study treatment are acceptable.
- **Serum Immunoglobulins:** IgG, IgM and IgA are required.
- **Genetic and Molecular Prognostic Markers:** Testing results are NOT required to proceed with study enrollment. Testing for *IGHV* mutational status (if not previously available) and GeneTrails analysis will be performed on a blood sample obtained on day 1 of the study (see Section 9 of the protocol).
 - CLL FISH panel (trisomy 12, deletion 11q, deletion 17p, deletion 13q), results acceptable if performed within 6 months prior to the first dose of study treatment, and if no intervening treatment occurred
 - ZAP-70 expression - results acceptable if performed at any time since diagnosis and will be documented where available, but not required
 - *IGHV* mutational status, if available - results acceptable if performed at any time since diagnosis. If this result is not available, testing for *IGHV* mutational status will be performed in [name] laboratory (see Section 9: Correlative studies).
- **Electrocardiogram (ECG):** 12-lead ECG must be performed at screening. QTc interval should be measured per institutional standard. ECGs will be repeated as clinically indicated.

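### Section 10.4 and the schedule tables do not carry the anti-HBc screen and HBV DNA testing that Section 5.3.2.1 requires

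*Combined protocol and SAP*

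**What the plan says.** **Section 10.4, Hepatitis Screening:** "hepatitis B surface antigen and hepatitis C antibody are required". Results up to 12 months old at first dose are accepted. Table 8 in Section 10.5 has one generic hepatitis serology row, ticked at screening, with no footnote. Tables 9, 10 and 11 have no hepatitis or HBV DNA row.

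**Section 5.3.2.1, Hepatitis B Reactivation:**

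- The screening instruction is "Screen all patients for HBV infection by measuring HBsAg and anti-HBc before initiating treatment with obinutuzumab". A positive result on either test counts as positive serology.
- Reactivation is reported in HBsAg-positive patients and "also in patients who are HBsAg negative but are hepatitis B core antibody (anti-HBc) positive".
- For patients with evidence of infection on either marker, sites are to "consult physicians with expertise in managing hepatitis B regarding monitoring, and consideration for HBV antiviral therapy".
- For anti-HBc-positive, DNA-negative patients who "have undetectable Hepatitis B viral DNA levels at screening", the rule is that "Hepatitis B viral DNA levels must be followed approximately every 4 weeks".
- The pointer to the action table reads "Guidelines for the management of hepatitis B reactivation are outlined in Table 1". Table 1 is the treatment description in Section 5.1; the hepatitis B action table is Table 4.

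**Exclusion 3.2.8** names active hepatitis B. It does not mention anti-HBc positivity alone.

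**The concern.** Two parts of one protocol specify the same safety screen differently. The part that sites use as a working list, 10.4 with Table 8, is the shorter one. HBsAg alone cannot identify a patient who is HBsAg negative and anti-HBc positive, and 5.3.2.1 names that group as one in which reactivation has occurred, with hepatic failure and death among the possible outcomes of reactivation.

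If such a patient is not identified, neither the specialist consultation nor the 4-weekly HBV DNA rule starts. Table 4 then has nothing to act on, because each of its rows begins from an HBV DNA level. What is at stake is patient safety and consistent conduct across sites, not the statistical analysis.

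**Working it through.** The plan gives no figure to reproduce here. The check is a comparison of sections, followed by a check of visit timing for the repair.

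**Comparison**

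| Item | 5.3.2.1 | 10.4 | Tables 8 to 11 |
|---|---|---|---|
| HBsAg, all patients | required | named | generic serology row (Table 8) |
| anti-HBc, all patients | required | not named | generic serology row (Table 8) |
| HBV DNA at screening, if anti-HBc positive | presupposed | absent | absent |
| HBV DNA about every 4 weeks, if anti-HBc positive and DNA negative | required | absent | absent |

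- Of the 2 HBV tests that 5.3.2.1 requires in all patients, 10.4 names 1.
- HBV DNA appears in 0 of 4 schedule tables.
- Of the 3 rows in Table 4, 3 start from an HBV DNA level.
- The Table 8 row could be read to include anti-HBc, but 10.4 is the only entry that itemises that row, and it leaves anti-HBc out.
- The 4-weekly DNA rule makes sense only if anti-HBc-positive patients can enrol, which agrees with the wording of 3.2.8.

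**Where can the repeat draws start?**

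Inputs: screening opens 30 days before first dose (10.1); first dose is Day -7; there is no day 0, so C1D1 is 7 days after Day -7 (5.1); cycles last 28 days. The screening DNA is assumed to be taken within the 30-day window of 10.1.

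Longest gap from screening DNA to first repeat = 30 + days from Day -7 to the repeat:

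- repeat at Day -7: 30 + 0 = 30 days
- repeat at C1D1: 30 + 7 = 37 days
- repeat at C2D1: 30 + 7 + 28 = 65 days

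Even if the screening DNA is drawn on Day -7 itself, a first repeat at C2D1 comes 7 + 28 = 35 days later. A schedule starting at C2D1 would therefore fail the rule it is meant to carry. A start at C1D1 stays within 28 days only if the screening DNA is taken no more than 28 - 7 = 21 days before Day -7; otherwise Day -7 is the better start.

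**How far do existing visits reach?**

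Taking C1D1 as day 1, Cn D1 falls on day 1 + 28(n - 1).

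- C1D1 to C6D1 (days 1 to 141): 6 visits, each 28 days apart, covering the obinutuzumab period.
- C7D1 to C12D1: 6 more. C13D1 and C14D1: 2 more. Total through C14D1 (day 365): 14.
- The next visit in Table 9 is C16D1, day 1 + 28 × 15 = 421, which is 56 days after C14D1.

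Four-weekly draws fit existing visits through C14D1 and not beyond. Table 10 has an end-of-treatment visit at 8 weeks and then 3-monthly visits, so it has no Day 1 visits to use.

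**The case against.** The strongest reply is that nothing is missing. Section 5.3.2.1 already orders anti-HBc in every patient. Section 10.4 says that two tests are required, not that only those two are, so a site can satisfy both sections at once. The protocol also leaves other conditional tests in the text, such as uric acid checks after rasburicase.

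Other controls exist too. Section 10.2.2 sets AST or ALT and bilirubin limits before each cycle from C2. Section 10.2 requires laboratory results to be reviewed before obinutuzumab. Table 6 holds both drugs for clinically significant Grade 3 or 4 non-hematologic toxicity. Section 5.3.2.1 itself requires immediate discontinuation of obinutuzumab on reactivation.

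Most of this stands, and it limits the point. A reader might infer that the protocol has no anti-HBc safeguard; the documents do not support that. However, the liver controls respond once liver tests are abnormal or toxicity has appeared, whereas serology and DNA are meant to find the patient beforehand. A site can complete every item named in 10.4 and still not measure anti-HBc.

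Two further inferences are tempting and should not be drawn as errors.

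- **The 12-month allowance.** It is longer than the 30 days in 10.1, and exclusion 3.2.1 permits rituximab until 4 weeks beforehand, so an accepted result can predate anti-CD20 therapy. Section 5.3.2.1 notes that "HBV reactivation has been reported for other CD20-directed cytolytic antibodies following completion of therapy". But the allowance is explicit and specific to this test. The FISH item in 10.4 does require that no treatment intervened, yet ZAP-70 and *IGHV* results in the same list are accepted from any time since diagnosis. This is a sponsor choice.
- **The end of monitoring.** No specific end is given for HBV DNA testing, but 5.3.2.1 does ask for clinical and laboratory monitoring for some months after obinutuzumab. That is imprecise, not absent.

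**Conclusion.** The inconsistency is real and should be corrected. Section 10.4 omits 1 of the 2 HBV tests that 5.3.2.1 requires in all patients. The HBV DNA test that 5.3.2.1 presupposes at screening and then requires about every 4 weeks is in neither 10.4 nor the schedule. The exposed group is HBsAg-negative, anti-HBc-positive patients at a site that works from 10.4 and Table 8.

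The documents give no prevalence and none is assumed, so the number of such patients cannot be stated. Nor do the documents show that any site missed the test or that any patient was harmed. There is no effect on the CR endpoint, the sample size or the error rates. The finding rests on the wording of the sections alone. The timing result also assumes that the screening DNA falls within the 30-day window.

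**What to change.** 1. **Section 10.4 and a Table 8 footnote.** Name three required serologies: HBsAg, anti-HBc and hepatitis C antibody. If anti-HBc is positive, require HBV DNA by PCR at screening, before the first dose.
2. **Tables 8 and 9.** Add a conditional footnote citing 5.3.2.1: in anti-HBc-positive patients with undetectable DNA at screening, HBV DNA about every 4 weeks. Draw it at existing visits, starting at Day -7 or C1D1 (not C2D1), then at each Day 1 visit while these remain 4-weekly, which is through C14. Do not put a Day 1 footnote in Table 10.
3. **Section 5.3.2.1.** Correct the table pointer from Table 1 to Table 4.

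**Cost.** This means protocol wording and footnotes, with no new visits through C14. Each patient has one more serology on screening blood. Each anti-HBc-positive, DNA-negative patient has one screening DNA assay and then 6 draws from C1D1 to C6D1, or 14 through C14D1 if entospletinib continues, plus one more if Day -7 is also used. Section 5.3.2.1 already mandates or implies all of these tests.

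**Optional, for the sponsor to decide:** repeat the hepatitis serology when anti-CD20 therapy has intervened since an older result, and state a specific end to DNA monitoring. Monitoring beyond C14, where visits are 56 days apart, would need draws outside the current schedule.

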- **Echocardiogram (ECHO):** will be performed at screening if clinically indicated. LVEF will be measured per institutional standard. Echocardiograms will be repeated as clinically indicated.
- **Computerized Tomography Scan (CT):** neck, chest, abdomen and pelvis are required with contrast. If contrast cannot be used for clinical reasons, a CT without contrast will be acceptable. Cheson criteria should be used to read each scan.

CT scans performed within 30 days of the first study treatment are acceptable for baseline assessment. Additional CT scans will be obtained at C4D1, C7D1, C10D1 (or \leq 72 h prior), C18D1 and C24D1, if appropriate, at the end of treatment visit, at 6 and 12 months after the end of treatment visit (\pm 7 days) and as clinically indicated thereafter. CT scanning may be performed at any point where it is suspected that disease progression has occurred between scheduled assessments.

NOTE: In subjects with NHL (FL, MZL, MZL) – PET-CT scans *may* be performed in place of CT scans at screening, during the study and at follow-up. However, the same modality should be used for each individual patient during the study.

NOTE: In subjects with LPL, CT scans on C4D1, C10D1 and during follow-up will be performed only if lymphadenopathy is present at screening, or if new lymphadenopathy develops during scheduled CT scans on C7D1 or the EOT visit.

- **Adverse Event Assessments:** Toxicities and adverse experiences will be assessed at each visit using the NCI Common Toxicity Criteria for Adverse Events 4.0. Adverse events will be reported and recorded as indicated in section 7 of this protocol.
http://ctep.cancer.gov/protocolDevelopment/electronic_applications/ctc.htm
- **Bone Marrow Aspirate and Biopsy** (optional at screening unless ANC<1,000/mm³ or platelets<50,000/mm³; optional at the end of treatment): will include cytogenetics and FISH, per institutional standards. Bone marrow biopsy performed within 6 months prior to the first dose of study treatment is acceptable.

Bone marrow biopsy should also be performed between 1 and 3 months at any time CR is suspected (e.g., C7D1, C10D1, C18D1, C24D1). An End-of-Treatment visit bone marrow biopsy will be performed between 1 and 3 months after the End of Treatment visit, unless study closure occurs. However, if CR is confirmed by bone marrow biopsy after C7D1, an EOT biopsy will not be performed.

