10.5 Schedule of Events

Table 8. SCREENING AND CYCLE 1

Visit/Cycle	Screening	Day -7 (Run-in Phase)	Cycle 1			
			1	2	8	15
Study Windows	-30 days	-3 days for screening tests to count for Day -7			±1 day	±1 day
Entospletinib		Days -7 to -1	Days 1-28			
Obinutuzumab			X	X	X	X
Informed consent	X					

Medical history	X	X	X	X	X	X
Concomitant medication (s)	X	X	X	X	X	X
Adverse events assessment		X	X	X	X	X
Height, weight	X	X				
Vital signs	X	X	X	X	X	X
ECOG performance status	X	X				
Physical examination	X	X				
12-lead ECG	X					
ECHO	X ^A					
Bone marrow aspirate and biopsy (includes biomarker aspirate)	X ^B					
Hematology	X	X	X	X	X	X
Chemistry	X	X	X ^C	X ^C	X	X
Hepatitis serologies	X					
aPTT, INR	X					
Serum immunoglobulins	X					
Reticulocyte count	X					
Direct antiglobulin test	X					
β 2-microglobulin	X					
Genetic and molecular prognostic markers	X ^D	X ^D				
Biomarker blood samples		X	X			
Serum/Urine pregnancy test	X					
Urinalysis	X					
CT neck, chest, abdomen and pelvis (with contrast when clinically acceptable) ^E	X					

KEY

^AECHO will be performed only if clinically indicated

^BBone marrow aspirate and biopsy is optional unless ANC<1,000/mm³ or platelets<50,000/mm³. Results acceptable if performed within 6 months prior to screening visit. Biomarker sample (10 mL aspirate) should be obtained (see 9.0 Correlative studies).

^COptional serum biochemistry/metabolic panel measurements may be considered by the investigator at the end of C1D1 and C1D2.

^DCLL FISH panel results acceptable if performed within 6 months prior to the first dose of study treatment, and if no intervening treatment occurred; ZAP-70 expression results acceptable if performed at any time since diagnosis and will be documented, but not required; IGHV mutational status - results acceptable if performed at any time since diagnosis. If this result is not available, testing for IGHV mutational status will be performed in [name] laboratory.

^EIn subjects with NHL (FL, MZL, MCL) – PET-CT scans *may* be performed in place of CT scans at screening, during the study and at follow-up. However, the same modality should be used for each individual patient during the study.

Table 9. CYCLE 2-

Visit/Cycle	Cycle 2-6	Cycles 7-12	Cycles 13, 14, 16, 18, 20 and then every two cycles until end of therapy
Cycle Day	1	1	1
Study Windows	+/- 3 days	+/- 3 days	+/- 7 days
Entospletinib^E	Days 1-28	Days 1-28	Days 1-28
Obinutuzumab	X		
Medical history	X	X	X
Concomitant medication (s)	X	X	X

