Adverse events assessment	X	X	X
, Weight	X	X	X
Vital signs	X	X	X
ECOG performance status	X	X	X
Physical examination	X	X	X
Hematology	X	X	X
Chemistry	X	X	
CT neck, chest, abdomen and pelvis (with contrast when clinically acceptable)^A	X^B (C4D1 or \leq72 h prior)	X^B (C7D1 and C10D1 or \leq72 h prior)	C18D1 and C24D1
Assessment of B-cell depletion		X (C7D1)	
Biomarker blood sample		X (C7D1)	
Bone marrow aspirate and biopsy (includes biomarker aspirate)^C		X	X
Overall response assessment^D	X	X	X^B

KEY:

^AIn subjects with NHL (FL, MZL, MCL) – PET-CT scans *may* be performed in place of CT scans at screening, during the study and at follow-up. However, the same modality should be used for each individual patient during the study.

^BIn subjects with LPL, CT scans on C4D1, C10D1 and during follow-up will be performed only if lymphadenopathy is present at screening, or if new lymphadenopathy develops during scheduled CT scans on C7D1 or the EOT visit.

^CIf radiographic and laboratory findings suggest that CR has been obtained, a bone marrow aspirate/biopsy should be obtained to confirm CR between 1 and 3 months after the corresponding CT, accompanied by a biomarker sample (10 mL aspirate) – see 9.0, Correlative studies

^DOverall response assessment should be performed when CTs or PET-CTs are performed

^ESubjects may continue entospletinib monotherapy beyond C12.

Table 10. End of Treatment and Follow-up prior to study closure

Visit/Cycle	EOT ^F	Follow up ^F	
Cycle Day	8 weeks after last dose of study drug	Every 3 months for the first year following EOT	Every 6 months for EFS thereafter
Study Windows	+/- 7 days	+/- 7 days	+/- 2 months
Medical history	X		
Concomitant medication (s)	X		
Adverse events assessment	X		
Height, weight	X		
Vital signs	X	X	
ECOG performance status	X	X	
Physical examination	X	X	X
MRD assessment, peripheral blood	X		
Bone marrow aspirate and biopsy; includes biomarker aspirate (all patients)	X^A		
Hematology	X	X	X
Chemistry	X	X	
Serum immunoglobulins	X		
CT neck, chest, abdomen and pelvis (with contrast when clinically acceptable)^B	X	X^{C,D}	
Overall response assessment^E	X	X	
Event-free survival assessment		X	X

KEY:

^AAn optional bone marrow aspirate/biopsy should be obtained between 1 and 3 months after End of Treatment visit, accompanied by MRD assessment and a biomarker aspirate. Exception: patients who underwent a bone marrow biopsy to obtain CR confirmation after 6 cycles of therapy will not undergo EOT bone marrow biopsy

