13.4.4 Interim Analyses and Stopping Rules

A 3+3 dose-escalation algorithm will be followed to insure safety. After the completion of the dose-determining part and prior to enrolling on the expansion cohort (phase II), safety and preliminary efficacy interim analysis will be performed.

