APPENDIX E LPL Assessment

Category	Finding
Laboratory	Serum monoclonal IgM > 0.5 g/dL Hemoglobin level < 10 g/dL Platelet count < 100 x 10 ⁹ /L
Laboratory + symptoms	Cryoglobulinemia with symptoms Hyperviscosity with symptoms
Physical Findings	Bulky adenopathy Organomegaly
Symptoms	Recurrent fevers Night sweats Weight loss Fatigue Symptomatic neuropathies
Organ Disease	Nephropathy Amyloidosis
Pathology	Disease Transformation

[figure not shown]
Definitions of Response for Waldenstrom's Macroglobulinemia

- Complete response (CR): Absence of serum monoclonal IgM protein by immunofixation; normal serum IgM level and complete resolution of extramedullary disease, i.e. lymphadenopathy and splenomegaly if present at baseline; morphologically normal bone marrow/aspirate and trephine biopsy.
- Very good partial response: Monoclonal IgM protein is detectable; $\geq 90\%$ reduction in serum IgM level from baseline; complete resolution of extramedullary disease, i.e. lymphadenopathy and splenomegaly if present at baseline; no new signs or symptoms of active disease.
- Partial response (PR): Monoclonal IgM protein is detectable; $\geq 50\%$ but < 90% reduction in serum IgM level from baseline; reduction of extramedullary disease, ie, lymphadenopathy and splenomegaly if present at baseline; no new signs or symptoms of active disease.
- Minor response: Monoclonal IgM protein is detectable; $\geq 25\%$ but < 50% reduction in serum IgM level from baseline; no progression in extramedullary disease, i.e. lymphadenopathy/splenomegaly if present at baseline; no new signs or symptoms of active disease.
- Stable disease: Monoclonal IgM protein is detectable; < 25% reduction and < 25% increase in serum IgM level from baseline; no new signs or symptoms of active disease.
- Progressive disease: $\geq 25\%$ increase in serum IgM level from lowest nadir (requires confirmation) and/or progression in clinical features attributable to the disease.

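### The IgM component of LPL response and progression cannot be assessed on treatment, because serum immunoglobulins are scheduled only at screening and end of treatment

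*Combined protocol and SAP*

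**What the plan says.** Section 11.2.3 sends LPL subjects, who are enrolled only in Phase I, to Appendix E. There, complete response needs "Absence of serum monoclonal IgM protein by immunofixation; normal serum IgM level and complete resolution of extramedullary disease", together with a normal marrow. Very good partial, partial and minor response and stable disease are each graded by percentage change in serum IgM from baseline. Progression is a rise of at least 25%, described as an "increase in serum IgM level from lowest nadir (requires confirmation) and/or progression in clinical features attributable to the disease".

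IgM comes from one test in section 10.4, the immunoglobulin panel: "IgG, IgM and IgA are required". It is not part of the chemistry panel. In section 10.5 the row "Serum immunoglobulins" is marked at screening in Table 8 and at EOT in Table 10. EOT falls "8 weeks after last dose of study drug".

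For imaging, section 10.4 says: "In subjects with LPL, CT scans on C4D1, C10D1 and during follow-up will be performed only if lymphadenopathy is present at screening". The same note gives a second trigger for those scans, namely adenopathy that first appears on the C7D1 or EOT scan. Section 10.4 also allows a CT whenever progression is suspected. The overall response assessment is listed in section 10.4 at C7D1, at EOT and in the first year afterwards; footnote D of Table 9 ties it to CT or PET-CT.

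The first of the two items numbered 3.1.4 exempts LPL from radiographically measurable disease and accepts a serum monoclonal IgM above 0.5 g/dL instead. Sections 5.4 and 10.2 make disease progression a reason to end treatment.

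**The concern.** The response definitions and the assessment schedule do not fit together. The definitions need a baseline IgM, serial values that reveal a nadir, a confirmatory value and, for CR, immunofixation. The schedule supplies a baseline and one value after treatment has ended.

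This matters most for a patient admitted on IgM alone. That patient may have no nodal disease to image, and the LPL note then removes the C4D1, C10D1 and follow-up CTs without putting an IgM measurement in their place. Because response assessment is tied to CT, the C4D1 and C10D1 assessments lapse as well. The C7D1 assessment still takes place, but without the measurement on which the categories rest.

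At stake are a usable description of LPL response in Phase I and the ability to see IgM progression while the patient is still taking drug. Investigators may order IgM off schedule, but nothing requires it or fixes its timing, so values from different patients would not be comparable.

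**Working it through.** The plan states no figure on this point, so the check sets the definitions against the schedule and counts.

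**Scheduled IgM per LPL subject (section 10.5)**

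| Period | Table | IgM scheduled |
|---|---|---|
| Screening | 8 | 1 |
| Run-in and cycle 1 | 8 | 0 |
| Cycles 2-12 and beyond | 9 (no such row) | 0 |
| EOT | 10 | 1 |
| Follow-up | 10 | 0 |
| EOT at study closure | 11 (modified EOT schedule) | 0 |

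The total is 2 values, or 1 for a subject still on drug at closure. The on-treatment count is 0. Immunofixation appears in none of these tables.

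**Time to the second value.** Inputs: run-in of 7 days, 28-day cycles, EOT 8 weeks (56 days) after the last dose.

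- First dose to the end of cycle 12: 7 + 12 × 28 = 343 days.
- First dose to EOT: 343 + 56 = 399 days, and 399 / 7 = 57 weeks.
- If the baseline was drawn at the limit of the 30-day screening window: 399 + 30 = 429 days between the two values.
- For a subject stopping after k cycles: 7 + 28k + 56 days. With k = 6 this is 231 days.
- C7D1 falls 7 + 6 × 28 = 175 days after first dose, with no IgM since screening.

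**What two values can show.** Let B be the screening IgM, N the on-treatment nadir and E the EOT value. The IgM limb needs E ≥ 1.25 × N and then a confirming value. The schedule yields B and E, but neither N nor the confirmation. Take a patient who just reaches partial response (N = 0.50 × B) and then just meets the 25% rise: E = 1.25 × 0.50 × B = 0.625 × B. Read against baseline, that is a 37.5% reduction, which Appendix E calls a minor response. The IgM progression is invisible in the scheduled data.

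**CT.** Through cycle 12 the general schedule has three on-treatment CTs (C4D1, C7D1, C10D1). An LPL subject without adenopathy keeps one of them, C7D1. The LPL note does not remove C18D1 and C24D1 for those who continue.

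**The case against.** A reader might infer that the LPL progression rule can never be met on treatment, and that a failing patient would therefore stay on both drugs. The documents do not support this. Progression in Appendix E is an and/or rule, and its clinical limb suffices alone. History, weight, physical examination and hematology are marked at every Table 9 visit. Section 10.4 requires examinations to document nodes, liver and spleen, and allows CT on suspicion. Obinutuzumab ends with cycle 6 in any case. Entospletinib beyond cycle 12 requires that the patient is benefiting and that the treating physician and sponsor-investigator approve.

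A reader might also infer that CT is simply omitted in LPL without adenopathy. It is not: C7D1 and EOT scans remain for every LPL subject.

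Nor is it right that LPL subjects can give no valid response. At the ordinary EOT visit both baseline and EOT IgM exist, so categories from very good partial response to stable disease can be graded against baseline. CR still lacks its named test.

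Finally, section 13.4.4 says that a "safety and preliminary efficacy interim analysis will be performed" before Phase II, and it is tempting to call that analysis compromised. It follows the dose-determining part, which turns on the run-in and cycle 1, so recent subjects may not have reached a response visit under any IgM schedule. No decision rule is attached to it.

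These points narrow the concern. They do not supply an on-treatment IgM, a nadir or a confirmation.

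**Conclusion.** The point holds in limited form. As scheduled, the IgM component of LPL response and progression cannot be assessed on treatment: an Appendix E response category cannot be properly assigned at C7D1, and an IgM progression cannot be established while the patient is on drug. A subject on drug at study closure has only the screening value, so IgM-based response cannot be graded even then.

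The reach is small. LPL is confined to Phase I, whose primary endpoint is dose-limiting toxicity and the MTD; the Phase II CR test is in CLL/SLL only. Neither is affected. The documents do not give the number of LPL subjects; I assume 0 to 3 of the 6 to 12 Phase I patients, so it could be none. The 399 days assumes 12 cycles without delay; it is shorter for early stoppers and longer for those who continue. The count of zero on-treatment values rests on the schedule as written and does not exclude tests ordered in routine care. The correction should be made because a stated schedule defeats a stated definition and the repair is cheap.

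**What to change.** Reconcile Appendix E with section 10.4 and Tables 8-11. For LPL subjects only:

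- Add serum IgM at the existing Day 1 visits that carry a response assessment in the general schedule (for example C4, C7, C10, C18 and C24), at the follow-up visits and at the closure EOT in Table 11. Keep the screening and EOT values.
- Require a repeat IgM to confirm any rise of at least 25% from nadir, and state when it is drawn.
- Require immunofixation when IgM is normal.
- Carry out the LPL response assessment at these visits whether or not a CT is done, and amend footnote D of Table 9 to say so.

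This changes what is measured and leaves the treatment rules as they stand. The cost is a schedule row and a few assays in a small number of patients. Hematology is already marked at the scheduled visits named, so blood is being drawn there. No scan or biopsy is added. The confirmatory repeat may need an extra draw if it cannot wait for the next visit.
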